#### *Randomization*

Subjects will be randomized to one of three injection groups: Group 1 will receive the control injection (Marcaine), Group 2 will receive a NSAID injection (Ketorolac & Marcaine), and Group 3 will receive a steroid injection (Kenalog & Marcaine).

Five to 10 minutes following injection, subjects will be asked how the injection changed shoulder symptoms by utilizing the Visual Analog Scale (VAS) and Single Assessment Numeric Evaluation (SANE).

Patients will be contacted by phone to complete a follow-up questionnaire 2 days after the injection as well as at 1, 2, and 4 weeks. The subjects will be followed up in clinic at 6 and 12 weeks, after the shoulder injection, which is standard clinical practice with completion of the outcomes questionnaire. Subjects will reach study completion at 12 weeks following injection.

#### *Subject Baseline Outcome Shoulder Questionnaire*

All data collected as part of this study will be through the use of standardized instruments. Once enrolled, subjects will be randomized, complete the baseline Outcome Shoulder Questionnaire, and then receive a shoulder injection in standard fashion under sterile conditions. Five minutes following the injection the subjects will again be asked questions as to the % improvement of their symptoms and VAS score will be obtained. At this time, baseline demographic information will be collected, in addition to measures of pain.

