### **3. Concise Summary of Project**

**3.1 Study Design:** The proposed study is a three arm, double-blinded, prospective randomized controlled clinical trial with follow-up immediately after the injection and at day 2, and weeks 1, 2, 4, 6, and 12. In this study we will compare the effectiveness of ketorolac compared to corticosteroid.

Ketorolac is an injectable solution which should be stored at 15 C to 30 C (59 F to 86 F) and protected from light. Marcaine (Bupivacaine) should be stored at room temperature, between 20 C to 25 C (68 F to 77 F). And Kenalog (triamcinolone) should be stored at controlled room temperature, 20°–25°C (68°–77°F), avoid freezing and protect from light. Do not refrigerate.[18]

Medications are stored in a locked cabinet at room temperature. The Research Team will prepare the appropriate injection medication according to group assignment at the time of the appointment. Injections will not be prepared beforehand. Injections will be prepared by inserting the syringe into both bottles and drawing the required amount. The syringe contents will be masked from the physician.

**Study Groups:** Subjects being seen for a rotator cuff injury will be randomized into one of three treatment groups pertaining to their pathology. The intervention will begin once the subject has consented and answered the Baseline Outcome Shoulder Questionnaire. The Baseline Outcome Questionnaire consists of the Visual Analog Score, American Shoulder and Elbow Score, Single Assessment Numeric Evaluation, Pittsburgh Sleep Quality Index, SF-12, range of motion and measure the subjects shoulder strength by using a

dynamometer, and questions pertaining to patient characteristics, injury characteristics, co-morbidities, patient history, medications, and demographics.

A dynamometer is a small, hand-held device which the subject presses against. By pressing against the device, it measures the strength of their shoulder.

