#### *Injection Procedure Description:*

The posterior aspect of the shoulder will be prepped in a sterile fashion with chlorhexidine scrub. The anatomic shoulder landmarks will be palpated under sterile conditions and using a standard posterior shoulder portal a subacromial injection will be given. For those subjects in which subacromial injection would be appropriate (i.e. rotator cuff disease) a 20 gauge needle is inserted posteriorly along the posterior border of the acromion, once contact is made with the underlying bone the needle is slid beneath the acromion and directed to the anterolateral aspect of the subacromial space then injection medication delivered. Dosages for each of the three group assignments will be as follows: Group 1 (control): 5 cc 0.25% Marcaine without epinephrine; Group 2 (ketorolac): 3 cc 0.25% Marcaine without epinephrine and 2 cc Ketorolac 30 mg/ml; Group 3 (kenalog): 4 cc 0.25% Marcaine without epinephrine and 1 cc kenalog.

The Research Team will prepare the appropriate injection medication according to group assignment and the syringe contents will be masked from the physician. Each injection will contain a total of 5 cc.

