## **9. RECRUITMENT METHODS and CONSENTING PROCESS:**

### *9.1 Screening*

The treating physicians will identify potentially eligible subjects from the UT Southwestern Ambulatory Outpatient Orthopaedic Surgery clinic and John Hopkins clinics: Johns Hopkins Orthopaedics, Johns Hopkins Community Physicians, and Southern Maryland Orthopaedic and Sports Medicine Division of Centers for Advanced Orthopaedics. Study Investigators and their research teams will assess subjects for the study and include a review of the medical record to ensure none of the study exclusion criteria are met. The study will be discussed with potentially eligible subjects.

*9.2 Recruitment:* Only those presenting for a shoulder evaluation at the UT Southwestern Ambulatory Outpatient Orthopaedic Surgery clinic and John Hopkins clinics: Johns Hopkins Orthopaedics, Johns Hopkins Community Physicians, and Southern Maryland Orthopaedic and Sports Medicine Division of Centers for Advanced Orthopaedics, who meet inclusion criteria will be recruited for potential participation in the study.

Informed consent will be obtained prior to initiation of the study. The physician will be involved in the consent conversation. The conversation will be initiated by the research team and physician together. The consent process will involve a dialogue. Specifically, patients and their families will be provided with a pamphlet describing the study, the risks and benefits of participation and what will be expected of them if they choose to participate.

Consent must be obtained from the patient in this study; no legally authorized representatives or surrogates may consent on behalf of the patient. This is due to the subjective nature of assessing pain. All recruitment materials will be provided in English.

9.3 Screening, enrollment, and informed consent process will take place in a private treatment area.

9.4 If a patient decides to withdraw from the study, he/she may do so at any point by informing the Principal Investigator in writing. A 'Note to File' must be inserted into the patient's chart and research file stating the patient formally withdrew from the study with the reason (if given). The patient will be assured that the medical care which they receive will not be affected should they elect to discontinue participation in the study.

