Randomization: Subjects will be recruited from the UT Southwestern Orthopaedic Surgery Clinic and John Hopkins clinics: Johns Hopkins Orthopaedics, Johns Hopkins Community Physicians, and Southern Maryland Orthopaedic and Sports Medicine Division of Centers for Advanced Orthopaedics, from patients who meet the inclusion criteria. As this study design will be prospective randomized double-blinded, we will utilize computer generated block randomization technique. After identifying a patient who meets the inclusion criteria by history, physical examination, and obtaining informed consent, HIPPA, health screen, and baseline measurements, subjects will be randomized into one of three cohorts: 1) Control (Marcaine injection), 2) NSAID injection (ketorolac & Marcaine injection), or 3) Steroid injection (kenalog & Marcaine injection). To ensure that the number of subjects is about the same in the three arms of the study, the randomization scheme will assign patients in a 1:1:1 ratio in randomly permuted blocks of assignments stratified by clinical center. Block size will be determined randomly and the patient will be the unit of randomization.

Enrollment and randomization results will be documented in the patient's chart according to protocol. The randomization allocation will be blinded to both the patient (initially) as well as the physician performing the injection and the investigator conducting statistical analysis of the results. Given the nature of this study looking at the effects of this intervention on multiple shoulder pathologies we anticipate approximately 200 subjects per diagnostic category would be needed for enrollment and complete follow-up.

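### The plan gives two opposite orders for randomisation and baseline assessment; one of them records the baseline of both primary outcomes after allocation

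*Combined protocol and SAP*

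**What the plan says.** Section 4, Subject Baseline Outcome Shoulder Questionnaire, lists the steps in sequence: "Once enrolled, subjects will be randomized, complete the baseline Outcome Shoulder Questionnaire, and then receive a shoulder injection". Randomisation comes first, baseline second, injection third.

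Section 14, Randomization, puts baseline first. Subjects are allocated after "obtaining informed consent, HIPPA, health screen, and baseline measurements, subjects will be randomized into one of three cohorts".

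The content of the baseline assessment is in section 3.1, Study Groups: "The Baseline Outcome Questionnaire consists of the Visual Analog Score, American Shoulder and Elbow Score, Single Assessment Numeric Evaluation". The same sentence adds sleep quality, SF-12, range of motion and dynamometer strength. Section 3.4 names VAS and ASES as the primary outcomes.

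On who knows the allocation, section 3.1 says: "The Research Team will prepare the appropriate injection medication according to group assignment at the time of the appointment". The injection procedure in section 4 repeats this and masks the syringe contents from the physician. Section 14 describes the allocation as "blinded to both the patient (initially) as well as the physician performing the injection and the investigator conducting statistical analysis of the results". Section 14.1 adds the study investigator to those who are blind. Neither list names the research team.

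**The concern.** A baseline taken before randomisation cannot be influenced by the assignment, because no assignment exists yet. Once allocation has happened, that guarantee depends on everyone who handles the baseline assessment being masked. Here the assessment carries the starting values of both primary outcomes, in a trial analysed by repeated measures. It also includes two measures, range of motion and strength, that depend on the person taking them. At least one member of the research team must know the group in order to draw up the syringe at that appointment.

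Several clinics take part, and a site cannot follow both orders. Different sites could reasonably adopt different ones. The section 4 order also allows a subject to be randomised and then have no baseline at all.

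**Working it through.** The point concerns the order of procedures, so the main check is to compare the sections.

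| Place | What it fixes | Does it settle baseline versus randomisation? |
|---|---|---|
| Section 4, baseline questionnaire | Randomise, baseline, inject | Yes: randomisation first |
| Section 14, Randomization | Consent, health screen, baseline, randomise | Yes: baseline first |
| Section 3.1, Study Groups | "The intervention will begin once the subject has consented and answered the Baseline Outcome Shoulder Questionnaire" | No: only places baseline before the intervention |
| Section 4, Enrollment | Baseline data collected after consent | No: randomisation is not mentioned in that step |
| Section 4, schedule of assessments | Baseline column is labelled as pre-injection | No: fits either order |

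Two places fix the order and contradict each other. The other three fit both.

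**What is exposed under the section 4 order.** The pre-injection column of the schedule holds VAS, ASES, SANE, PSQI, SF-12, range of motion and dynamometer: 7 measures. Both primary outcomes are among them (2 of 2).

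**Who is masked.** Sections 14 and 14.1 together cover the patient, the injecting physician, the study investigator and the investigator doing the analysis. The research team prepares the injection by group. The plan does not say who administers the questionnaire or takes the range-of-motion and strength readings, or that this person is masked.

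**Effect on the design calculation.** The inputs in section 14.2 are a difference of 12, SD 23, alpha 0.05 and power 0.8. Sidedness is not stated; two-sided is assumed.

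- Normal approximation: n = 2 × (1.960 + 0.842)² × 23² / 12² ≈ 57.7, so 58 per arm.
- Two-sample t-test: 58.64, so 59 per arm. This reproduces the plan's 59, with power 0.802.

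None of these inputs depends on when baseline is taken, so correcting the order leaves sample size, alpha and power as they are.

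**Size of any bias.** It cannot be calculated from the documents. They give no basis for a shift in baseline. Section 14.1 does not say whether baseline enters as a change score, as a covariate or as one of the repeated measures. Section 14.2 does not say which scale the 12 and 23 belong to.

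**The case against.** The best defence is that section 4 is loose narrative. The same paragraph also places collection of baseline demographics after the injection, which does not fit the rest of the plan. A reader looking for the randomisation procedure would go to section 14, which is explicit and gives the safer order. Every version keeps baseline before injection. This lowers the severity but does not remove the conflict: the section 4 sentence is a step-by-step instruction, under the heading that staff would consult for this questionnaire.

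The second defence is that any route to bias is narrow. The patient does not know the group, VAS and part of ASES are self-reported, and no drug has yet been given. The documents do not say that the person who prepares the syringe also collects baseline. All of this stands. It protects the staff-measured items less well, and ASES also has a physician-assessed section. It is equally true that reordering does nothing about who collects follow-up data.

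Two stronger readings are tempting, and the documents support neither.

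- *A reader might infer that the primary comparison is biased.* Nothing in the plan shows this. It would need an unmasked assessor and an effect of that knowledge on the baseline readings, and neither is documented.
- *A reader might infer that ineligible subjects would be dosed, or that exclusions would erode power.* Eligibility is mainly settled before this step. Screening must "include a review of the medical record to ensure none of the study exclusion criteria are met", the chart is abstracted for medications and co-morbidities, and staff re-check eligibility at consent. The questionnaire precedes the injection in either order. Some medical history does come from the questionnaire, so a late discovery is possible, but the documents give no rate. Losing one evaluable subject from an arm of 59 would move power only from 0.802 to 0.796 (59 versus 58 in that calculation).

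**Conclusion.** The contradiction is certain: two current sections give opposite orders and nothing else in the plan resolves them. Under the section 4 order, baseline VAS and ASES, and staff-measured range of motion and strength, are obtained after allocation, at a visit where some staff know the group and no masked baseline assessor is specified. The consequence is a possible route to bias that could have been closed, not a demonstrated bias. Its size is unknown, and sample size and power are unaffected. Severity is minor, and the correction is a free improvement. The conclusion assumes only that a site might follow section 4 as written.

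**What to change.** Amend the section 4 sentence to the order already in section 14:

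1. Consent.
2. Health screen and confirmation of eligibility.
3. Baseline questionnaire and measurements, with a check that no answer meets a section 7 exclusion.
4. Randomisation.
5. Injection.

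The health screen should stay ahead of baseline, as in section 14, so that the amendment does not create a new mismatch.

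The cost is a wording change. The questionnaire is already completed before the injection, so no visit or test is added. The only extra step is a brief look at the answers before allocation.

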#### *Injection Procedure Description:*

The posterior aspect of the shoulder will be prepped in a sterile fashion with chlorhexidine scrub. The anatomic shoulder landmarks will be palpated under sterile conditions and using a standard posterior shoulder portal a subacromial injection will be given. For those subjects in which subacromial injection would be appropriate (i.e. rotator cuff disease) a 20 gauge needle is inserted posteriorly along the posterior border of the acromion, once contact is made with the underlying bone the needle is slid beneath the acromion and directed to the anterolateral aspect of the subacromial space then injection medication delivered. Dosages for each of the three group assignments will be as follows: Group 1 (control): 5 cc 0.25% Marcaine without epinephrine; Group 2 (ketorolac): 3 cc 0.25% Marcaine without epinephrine and 2 cc Ketorolac 30 mg/ml; Group 3 (kenalog): 4 cc 0.25% Marcaine without epinephrine and 1 cc kenalog.

The Research Team will prepare the appropriate injection medication according to group assignment and the syringe contents will be masked from the physician. Each injection will contain a total of 5 cc.

#### *Follow-up Interviews*

Subjects will be contacted by phone to obtain VAS score at day 2, and weeks, 1, 2, and 4 after the injection. They will be instructed to return to clinic at routine follow-up intervals at 6 and 12 weeks after the injection and will again be asked to complete the Outcome Shoulder Questionnaire containing VAS, ASES, SF-12, PSQI scores. Subjects range of motion and shoulder strength will also be collected. All data collected with regards to this study will be kept in a password-protected database, which will only be accessible, by study investigators and the research team.

Study subjects who do not respond to the follow-up phone calls in a timely manner, will be mailed a paper copy of the Follow-up Outcome Shoulder Questionnaire and/or emailed a website link to the same questionnaire on [www.surveymonkey.com](http://www.surveymonkey.com)

	Baseline Shoulder Questionnaire			Follow-up					
	Med Record Review	Pre-Injection	5 Minutes Post Injection	Day 2	Week 1	Week 2	Week 4	Week 6	Week 12
Visual Analog Score (VAS)		X	X	X	X	X	X	X	X
American Shoulder and Elbow Score (ASES)		X						X	X
Single Assessment Numeric Evaluation (SANE)		X	X					X	X

Pittsburgh Sleep Quality Index		X					X	X
SF-12		X					X	X
Range of Motion		X	X				X	X
Dynamometer measurements		X	X				X	X
Pt Characteristics	X							
Injury Characteristics	X							
Co-Morbidities	X							
Pt Hx	X							
Meds	X							
Demographics	X							

4.3 Each phone follow-up should take approximately 10 minutes each and the standard follow-up visits should each take approximately 30 to 45 minutes.

4.4 At each time frame, the subjects will be asked to complete a questionnaire. Blood and tissue samples will not be collected for this study.

4.5 Subjects will be billed for the services received whether they participate in the study or not.

4.6 The only change in clinic practice of shoulder disorders as part of this study protocol will be the randomization of injection medication they will be receiving. Subjects will be prescribed physical therapy as is standard for the treatment of shoulder disorders.

We believe the ketorolac injection will be equivalent with regards to pain relief as the corticosteroid injection. Additionally, with the results of this study we can provide an alternative pain relief modality that is safe and effective for patients with shoulder disorders. Furthermore, with the results obtained from this study we can provide patients who may have medical comorbidities such as uncontrolled diabetes mellitus that are contraindicated for corticosteroid injections, an effective treatment option.

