### 3.4 Independent Variable: One of three injection protocols.

#### Dependent Variables

- Primary Outcome Variable:
  - Visual Analog Scale
  - American Shoulder and Elbow Score
- Secondary Outcome Variable:
  - Single Assessment Numeric Evaluation (SANE)
  - Pittsburgh Sleep Quality Index
  - SF-12

**Functional Outcome:** Visual Analog Scale (VAS) is utilized to measure level or intensity of pain. The scale consists of a horizontal (HVAS) or vertical (VHAS) line, usually 10 cm in length [22] with a descriptor at both ends; the left side reading “no pain at all” and the right side reading “worst pain imaginable.” While this scale is very subjective, patients have an easier time reporting pain on a continuum rather than jumping from categories of none, mild, moderate [23] or severe.

**American Shoulder and Elbow Score (ASES):** is a standardized, 17 item [24], patient self-report tool, which can be completed in about 3 minutes. The patient self-reported section consists of three sections: pain, instability, and activities of daily living. The tool also consists of a physician assessment which includes range of motion, signs, strength, and instability.[25]

**Single Assessment Numeric Evaluation (SANE):** “is an outcome measurement tool used to record the patient’s self-reported function [26]. It is implemented on a scale of 0-100 and correlated with a scale of function from 0-100%. The 100% representing full function (or function prior to injury) and 0% representing no function.”

**Pittsburgh Sleep Quality Index (PSQI):** is a standardized measure for quality of sleep. The tool consists of 24 questions which differentiate “good” and “poor” sleepers and is easy to use for both the patient and the researchers.[27]

**SF-12:** is a standardized general health survey which measures physical and mental health.

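### The primary VAS is described as a marked line but is collected by phone at four of six follow-ups, with no phone scoring method, contact window or rule for late forms, so formats and dates can mix

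*Combined protocol and SAP*

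**What the plan says.** Section 3.4 lists the VAS, with the ASES, under "Primary Outcome Variable". It describes the instrument as follows: "The scale consists of a horizontal (HVAS) or vertical (VHAS) line, usually 10 cm in length". It adds worded ends, and prefers a continuum to pain categories.

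The Follow-up Interviews part of section 4 sets the route of collection:

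- Early contacts: "Subjects will be contacted by phone to obtain VAS score at day 2, and weeks, 1, 2, and 4". The Randomization part of section 4 also has these contacts by phone.
- Later contacts: "They will be instructed to return to clinic at routine follow-up intervals at 6 and 12 weeks after the injection", where the full questionnaire, including the VAS, is completed.
- Missed calls: "Study subjects who do not respond to the follow-up phone calls in a timely manner, will be mailed a paper copy" of the follow-up questionnaire, "and/or emailed a website link to the same questionnaire on" a survey website.

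Section 14.1 analyses the dependent variables with a repeated-measures analysis of variance. It mentions neither the mode of collection nor the actual date of assessment.

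**The concern.** A line cannot be marked by voice. The documents neither say how a caller turns the line into a score nor provide for subjects to mark a sheet at home. The fallback forms go out only after a call has failed, and no time limit is set for sending, returning or accepting them. Three things are at stake.

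1. **Time course.** Baseline is in clinic, day 2 to week 4 by phone, and weeks 6 and 12 in clinic again. If the format follows the route, then change from baseline to any phone contact, and the step from week 4 to week 6, cannot be separated from the change of mode.
2. **Mixing within a visit.** Under one nominal visit, some scores may come by phone, some on paper and some by web, on different dates. Day 2 and week 1 are five days apart, so a misdated form matters most there.
3. **Noise.** The closing text of section 4 expects ketorolac to match the steroid for pain relief, while section 14.2 powers a test of difference. Measurement noise makes a non-significant result more likely, and that result could be misread as support for equivalence.

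**Working it through.** **Step 1. Count the readings.** From the schedule table under Follow-up Interviews:

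| VAS reading | Route | Scoring method for that route |
|---|---|---|
| Pre-injection, 5 minutes after | Clinic | Line, by the general description in 3.4 |
| Day 2, weeks 1, 2, 4 | Phone | None given |
| Same contacts, call missed | Paper and/or web | None given; no time limit |
| Weeks 6, 12 | Clinic | Line, by the general description in 3.4 |

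Phone covers 4 of the 6 follow-up columns, 4 of 7 if the reading just after injection is counted, and 4 of all 8 readings.

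**Step 2. Reproduce the plan's sample size**, to fix the yardstick. Inputs from section 14.2: difference 12, SD 23, power 0.80, alpha 0.05.

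n = 2(1.960 + 0.842)² × 23² / 12² = 2 × 7.85 × 529 / 144 = 57.7, so 58 per group by the normal approximation. The noncentral t gives power 0.796 at 58 and 0.802 at 59, so the stated 59 per group reproduces (two-sided). Section 14.2 does not say which outcome or scale the 12 and 23 belong to. Steps 3 and 4 assume that they are pain points.

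**Step 3. Bias in an arm contrast at one visit.** Let b be the mean shift in score when the fallback replaces the call, and q the difference between arms in the share of subjects who use it. Bias = b × q. The documents give neither, so both are assumptions:

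| b (points) | q = 0 | q = 0.10 | q = 0.20 |
|---|---|---|---|
| 5 | 0 | 0.5 (4% of 12) | 1.0 (8%) |
| 10 | 0 | 1.0 (8%) | 2.0 (17%) |

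The zero at q = 0 holds for a shift b that is the same in all arms. If the arms differ in time course, late forms filed under an earlier visit also blend the contrasts of two dates.

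**Step 4. Precision, as illustration only.** Assume that mode and timing add an independent SD s to the 23. The total SD is √(23² + s²). Power is by normal approximation at 59 per group; the last column is the n per group for 80% power.

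| s | Total SD | Power | n per group |
|---|---|---|---|
| 0 | 23.00 | 0.81 | 58 |
| 5 | 23.54 | 0.79 | 61 |
| 10 | 25.08 | 0.74 | 69 |
| 15 | 27.46 | 0.66 | 83 |

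No value of s can be read from the documents, and the SD of 23 may already contain some such noise. The table shows how power responds to s; it does not estimate the loss in this trial.

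**The case against.** **The mixing is not stated.** Section 3.4 reads as a general account of the VAS, not an operating instruction: it leaves the orientation open and the length only usual. The questionnaire is not in the documents, and the web version is said to be the same as the mailed one. One numeric item in every mode would fit the text. A reader might infer that clinic visits use a line and calls a spoken number, but the documents say neither, and they do not rule out a scale sheet kept at home. This stands, and it limits the point to what the text permits. The gap remains: the only description given is of a line, and the text offers no way to take it by phone.

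**Late is an inference.** A reader might conclude that a form posted after a missed day-2 call is analysed as day 2. No delivery time or labelling rule is given, and an emailed link can be answered the same day. What stands is narrower: a paper form posted only after a failed day-2 call cannot give a true day-2 score, and nothing prevents it from being filed as one.

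**The arms are treated alike.** The scheduled routes are the same in all three arms, and the aim is a comparison between arms. The ASES, the other primary outcome, is collected only in clinic. All of this stands and keeps the consequence modest. It does not cover unequal use of the fallback.

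**A fixed percentage for lost precision is tempting.** One could assume that switching mode lowers the correlation with baseline. If it fell from 0.6 to 0.55, 0.5 or 0.4, the baseline-adjusted variance, proportional to 1 − ρ², would rise by 9%, 17% or 31% (0.6975, 0.75 or 0.84, each over 0.64). But section 14.1 names no baseline covariate, the sample size is an unadjusted comparison of two means, and no correlation is given. With total SD fixed, an unadjusted comparison loses nothing, while change-score variance, 2(1 − ρ), rises by 25% for 0.6 to 0.5. No single figure is supported.

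**Conclusion.** The point holds as a weakness in how a primary outcome is specified. Following the text as written can mix formats across visits, and formats and dates within a visit. The scheduled phone/clinic split confounds mode with time and with change from baseline, but it need not bias a same-visit arm contrast. A reader might go on to infer that the arm comparison is biased; the documents do not support that. Bias needs unequal fallback use, or late forms filed under the wrong visit while the arm difference is changing over time. Under the assumed ranges in the bias table it runs from 0 to 2.0 points against a planned difference of 12. The loss of precision is plausible, but its size cannot be derived from the documents. This is a minor point, worth acting on because the remedy is cheap.

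**What to change.** - **One item.** Use a single numeric pain rating with identical wording and anchors at every contact, including baseline, in clinic and by phone, paper or web.
- **One scale.** Choose a scale consistent with section 14.2 and name it there. An SD of 23 cannot belong to a 0–10 item. If the inputs are pain points on 0–100 (an assumption), a 0–10 item would need them restated as SD 2.3 and difference 1.2, with the same ratio and the same n.
- **Dates and modes.** Record the mode and completion date of every score, and set a window for each contact.
- **Fallback.** For day 2 and week 1, use the phone or the web link, not the post. Do not label an out-of-window score with the missed nominal visit; keep it under its actual date.
- **Analysis.** Use a method that keeps subjects who miss a visit, such as a mixed model for repeated measures. Classical repeated-measures analysis of variance can drop a subject with any missing visit. Add a sensitivity analysis by mode and actual date.

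The cost is form wording and a few sentences in sections 3.4, 4 and 14, with no change to treatment or visits. Scores become less directly comparable with published line-VAS results, and a few more early values will be missing. If enrolment has begun, recording mode and date and adding the sensitivity analysis are still feasible.
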